6.3. Imputation Methods

The primary analyses of efficacy data (IOP) will employ multiple imputation methods using Monte Carlo Markov Chain approach to impute missing data and using last time-consistent observation carried forward (LOCF) to impute data for time points after a subject's primary study eye is prescribed IOP-lowering drops.

Sensitivity analyses, to determine robustness of results, will be performed using Monte Carlo Markov Chain approach to impute non-monotone missing information and pattern mixture models control-based pattern imputation for monotone missing information (including subjects who drop out and data for time points after a subject's primary study eye is prescribed IOP-lowering drops), LOCF to impute both missing data and data after a subject's primary study eye is prescribed IOP-lowering drops, and baseline time-consistent observation carried forward to impute both missing data and data after a subject's primary study eye is prescribed IOP-lowering drops and observed data only. Additionally, sensitivity analyses will be performed on the per protocol population using observed data only.

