All subjects will undergo follow-up visits at 2, 4, 6, 8, 10, and 12 Weeks. If at any visit, the Investigator deems it necessary to initiate IOP-lowering drops as rescue therapy due to an increase in IOP, the subject will be considered an efficacy failure and will be followed through the remainder of the study for safety. If still present, the intracanalicular depot will not be removed. IOP measurements taken through the remainder of the study will be excluded from the efficacy analyses.

For any subject, if at any point the intracanalicular depot is removed bilaterally by the Investigator for an adverse event or subject discomfort, the subject will be exited from the study at that visit. If the intracanalicular depot needs to be removed from only one eye, the depot from the contralateral eye will not be removed and the subject will be followed per the study schedule for safety.

Intracanalicular depots that are removed due to subject withdrawal or an undesired reaction at any point in the study will not be replaced.

For subjects with Early Loss of Intracanalicular Depot Prior to the 6 Week Visit:

At any visit prior to the 6 Week Visit, if the intracanalicular depot is not visualized in one or both eyes by the Investigator, the Investigator will insert a new intracanalicular depot in the respective eye(s) after confirming patency. For any depot replacements, IOP assessments should be completed prior to replacement. The subject will continue to return for follow-up visits per the study schedule through the 12 Week Visit. The number of depot replacements will be tracked and documented on the appropriate electronic Case Report Form (eCRF).

For subjects with Early Loss of Intracanalicular depot from the 6 Week Visit prior to the 12 Week Visit:

At any visit from the 6 Week Visit prior to the 12 Week Visit, if the intracanalicular depot is not visualized in one or both eyes by the Investigator, the Investigator will insert a new intracanalicular depot in the respective eye(s) after confirming patency. For any depot replacements, IOP assessments should be completed prior to replacement. The subject will return for follow-up visits through the 12 Week Visit and then at the 20 Week Visit. Depots replaced between the 6 Week Visit and the 12 Week Visit will not be

removed at the 12 Week Visit. The first attempt to remove these depots will be at the 20 Week Visit. The number of depot replacements will be tracked and documented on the appropriate eCRF.

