The primary analyses of efficacy data (IOP) will employ multiple imputation (MI) methods using the Markov Chain Monte Carlo (MCMC) approach to impute missing data and using the last time-consistent observation carried forward (LOCF) to impute data for time points after a subject's primary study eye is prescribed IOP-lowering drops as rescue therapy.

Sensitivity analyses, to determine robustness of results, will be performed using the MCMC approach to impute non-monotone missing information and pattern mixture models control-based pattern imputation for monotone missing information (including data for subjects who drop out prior to the 12 Week Visit and data for time points after a subject's primary study eye is prescribed IOP-lowering drops), LOCF to impute both missing data and data after a subject's primary study eye is prescribed IOP-lowering drops, baseline time-consistent observation carried forward (BOCF) to impute both missing data and data after a subject's primary study eye is prescribed IOP-lowering drops and using observed data only (excluding data after a subject's primary study eye is prescribed IOP-lowering drops as rescue therapy). Additionally, sensitivity analyses will be performed on the PP population using observed data only (excluding data after a subject's primary study eye is prescribed IOP-lowering drops as rescue therapy).

For time-consistent imputations, IOP values missing at an 8AM time point will only be imputed with the IOP value from a previous 8AM time point (last or baseline). Imputations at 10AM and 4PM will be performed similarly.

Definition of Baseline

For IOP, the baseline measure will be defined as the last non-missing time-consistent measure prior to initiation of investigational treatment and after washout of previous IOP medication. In most cases this will be the measure of IOP at Baseline Visit 2. For all other variables, baseline will be defined as the last non-missing measure prior to initiation of investigational treatment. Change from baseline will be calculated as follow-up visit – baseline visit.

Data Analysis Conventions

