Sensitivity analyses for the primary efficacy endpoint include both linear models of IOP and 2-sample t-tests presented on the FAS population using (1) MI approach using MCMC to impute non-monotone missing information and a pattern mixture model control-based pattern imputation for monotone missing information to impute both missing data and data after a subject's primary study eye is prescribed IOP-lowering drops as rescue therapy, (2) using LOCF to impute both missing data and data after a subject's primary study eye is prescribed IOP-lowering drops as rescue therapy, (3) using BOCF to impute both missing data and data after a subject's primary study eye is prescribed IOP-lowering drops as rescue therapy, and these analyses using observed data only (excluding data after a primary study eye is prescribed rescue therapy) for the (4) FAS and (5) per protocol populations.

For multiple imputations using a control-based pattern-mixture model, a process will be used that is similar to multiple imputations using MCMC. Twenty "complete" (imputed) datasets will be produced and analyzed. Results from the analyses on the twenty "complete" datasets will be combined for presentation through the use of SAS® PROC MIANALYZE. Time point specific baseline IOP will be used as a covariate, and treatment will be the main effect factor. A separate model will be fit for each visit/time point combination. Monotone missing information refers to data missing from any visits beyond a subject's final visit (at which IOP is assessed) up to and including the 12 Week Visit. Non-monotone missing information refers to data from missed visits between any two visits at which IOP is assessed. First LOCF will be used to impute data for time points after a subject's primary study eye is prescribed IOP-lowering drops. Then MCMC will be employed to impute any non-monotone missing information using the code:

```
PROC MI DATA = indata SEED = 3335891 OUT = mondata NIMPUTE=1;  
BY TMPTN;
```

```
MCMC INITIAL = EM IMPUTE = MONOTONE;
VAR trt baseline WV2 WV4 WV6 WV8 WV10 WV12;
RUN;
```

where

- *indata* is the name of the input dataset;
- *mondata* is the name of the output dataset;
- *nimpute* is the number of imputations;
- *trt* is the name of the treatment group variable in numeric format;
- *baseline* is the average IOP at baseline;
- *WV2* is the IOP value for the 2 Week visit;
- *WV4* is the IOP value for the 4 Week visit;
- *WV6* is the IOP value for the 6 Week visit;

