Mean change from baseline IOP and mean percent change from baseline IOP will be analyzed similarly to the primary endpoint analysis, including all sensitivity analyses. (If a subject is missing a baseline IOP value, or if Baseline Visit 2: 4PM IOP is measured after insertion, change from baseline and percent change from baseline are not calculated.) As described above, these analyses involve linear models of the response variables on the FAS population using various combinations of imputation methods [(a) MCMC for missing data, LOCF for timepoints after rescue therapy has been initiated; (b) MCMC for non-monotone missing, pattern mixture models for monotone missing; (c) LOCF for both missing and “rescue” time points; and (d) BOCF for both missing and “rescue” time points] as well as inference on observed data confined to the FAS and Per Protocol populations.

Additional Analyses

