This SAP differs from the protocol-stated analysis in three respects:

- (1) The statement, “Intent-to-Treat (ITT): The ITT population will include all randomized subjects with a primary study eye in which an intracanalicular depot was inserted. Analysis on the ITT population will be used as the primary efficacy analysis and will be performed for all efficacy endpoints, analyzing subjects under the treatment to which they were randomized” in the protocol has been changed to “The Full Analysis Set (FAS) will include all randomized subjects with depots inserted in both eyes. Analysis on the data for the primary study eye in the FAS will be used as the primary efficacy analysis and will be performed for all efficacy endpoints, analyzing subjects under the treatment to which they were randomized.” The rationale behind this change is that the protocol allows for subjects with successful insertion of a depot in only one eye to be treated with IOP-lowering drops, which may have a systemic effect on both eyes or lead to bilateral treatment with IOP-lowering drops.
- (2) No subject visualization of depots is required.
- (3) The protocol (5.6) states, “At the conclusion of the 12 Week visit, if both eyes no longer have the depot present or depots have been removed bilaterally, the Investigator may be unmasked to the treatment assignment of the subjects who were assigned to OTX-TP or PV as those subjects may require IOP-lowering drops.” Due to the logistics involved and the potential for bias, the sponsor has determined that investigators and investigative site staff will not be unmasked until the end of the study.
- (4) An interim analysis as the primary efficacy analysis was planned as part of the protocol. As the study proceeded, the sponsor determined that the interim would not be necessary as accrual had been sufficient to shorten the time between the interim and final analyses.

Any changes to the planned analyses after unmasking and the final analysis will be described in the clinical study report.

20. References

US Federal Register. (1998) International Conference on Harmonization; Guidance for Industry: Statistical Principles for Clinical Trials. Department of Health and Human Services: Food and Drug Administration. Federal Register, Vol. 63, No. 179, September 16, 1998, page 49583. (E9)

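### The control-based sensitivity analysis is said to cover data after rescue drops, but its algorithm fills those data by LOCF first, so they keep their primary-analysis values

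*SAP*

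**What the plan says.** Three places set the scope of the control-based analysis, and all include rescue.

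- Protocol 6.3 specifies "pattern mixture models control-based pattern imputation for monotone missing information (including subjects who drop out and data for time points after" the study eye is prescribed IOP-lowering drops.
- SAP v2.0 section 9 (Missing Data and Imputation Methods) repeats this: "monotone missing information (including data for subjects who drop out prior to the 12 Week Visit and data for time points after" rescue.
- SAP v2.0 section 13 (Primary Analysis), sensitivity analysis (1), applies the method both to missing data and to data after rescue.

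The algorithm, later in the same subsection, opens with "First LOCF will be used to impute data for time points after" rescue. MCMC then fills intermittent gaps, and a control-based MNAR step fills what is still monotone missing. That term is defined there too: "Monotone missing information refers to data missing from any visits beyond a" subject's last visit with an IOP assessment.

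Three other places bear on the point.

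- SAP section 4 keeps rescued subjects in follow-up, but "IOP measurements taken through the remainder of the study will be excluded from the efficacy analyses".
- The Secondary Analysis text summarises this method as "b) MCMC for non-monotone missing, pattern mixture models for monotone missing", without mentioning rescue, although its entries for methods (a), (c) and (d) all mention it.
- SAP section 19 opens with "This SAP differs from the protocol-stated analysis in three respects" and lists four items. A change to protocol 6.3 is not among them.

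SAP v1.0 carries the same conflict.

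**The concern.** The scope statement and the algorithm cannot both be followed. Two programmers could produce different versions of analysis (1), each citing the SAP. If the algorithm is followed, the pattern-mixture table will be read as showing robustness to rescue handling, which that table never varied.

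This matters because the SAP treats a rescued subject as an efficacy failure, and analysis (1) is the only planned analysis that would give such subjects control-like values. The primary result and the success rule are not at stake.

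**Working it through.** **Tracing the cells.** Take a subject rescued at Week 6 and followed to Week 12.

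| Step | Primary analysis | Analysis (1), as in the algorithm | Analysis (1), as in its stated scope |
|---|---|---|---|
| Post-rescue cells | LOCF | LOCF | set to missing |
| MCMC | cells already filled | cells already filled | not filled here |
| Control-based step | not used | cells already filled | filled from the control model |
| Final value | LOCF | LOCF | control-based |

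The first two columns end alike, and in simulation the post-rescue values were identical in every run. Deleting the LOCF sentence might not be enough. Rescued subjects still have IOP assessed at later visits, so read literally the definition of monotone missing leaves their post-rescue cells out.

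**Inputs from the documents.** SD 3.75 mmHg, difference 1.5 mmHg, 294 and 196 evaluable, 330 and 220 randomized, 10% dropout. The SAP's power figure reproduces on these inputs. SE = 3.75 × √(1/294 + 1/196) = 0.346; power per time point is 0.991; 0.991⁹ is about 0.92, against a stated figure above 90%. The smallest significant difference at one time point is 1.96 × 0.346 = 0.68 mmHg.

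**Assumed, because the documents do not say.** Rescue rates, correlation between visits, and the rate of intermittent missing data.

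**Simulation 1.** 330/220 subjects, 600 replicates, correlation 0.6, IOP-driven rescue at Week 6, control model conditioned on earlier visits. Week 12 8AM difference (OTX-TP minus PV), in mmHg; shifts are computed before rounding:

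| Rescue OTX-TP / PV | LOCF first | Control-based after rescue | Shift |
|---|---|---|---|
| 5% / 10% | -1.51 | -1.41 | 0.09 |
| 10% / 20% | -1.54 | -1.39 | 0.15 |
| 15% / 30% | -1.54 | -1.36 | 0.18 |

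In these three scenarios LOCF-first differs from the primary analysis by only 0.05 to 0.06, all of it from dropout. Variations:

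- correlation 0.7 to 0.4: shift 0.07 to 0.25
- rescue spread over Weeks 2 to 10: 0.11 to 0.30
- step 2 regressing on baseline only, as the SAP code does: 0.17 to 0.41
- equal rescue (10%/10%): 0.06
- more rescue on OTX-TP (10%/5% or 20%/10%): 0.00 to 0.03

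**Simulation 2.** Rescue whenever IOP exceeds a threshold (30, 28, 27 or 26 mmHg), 300 trials per setting, one imputation per trial:

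| Rescue OTX-TP / PV | Primary | LOCF first | Control-based after rescue | Shift |
|---|---|---|---|---|
| 1.5% / 4.4% | -1.651 | -1.618 | -1.474 | 0.144 |
| 6.0% / 13.1% | -1.745 | -1.717 | -1.418 | 0.299 |
| 10.2% / 20.7% | -1.857 | -1.826 | -1.416 | 0.410 |
| 16.6% / 30.2% | -1.853 | -1.812 | -1.380 | 0.432 |

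The direction is the same, and every average estimate stays beyond 0.68 mmHg.

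**The code.**

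- Step 1 is "PROC MI DATA = indata SEED = 3335891 OUT = mondata NIMPUTE=1", and step 2 makes 20 draws from that one file, so intermittent values carry no between-imputation variance. At Week 6, with 2%, 5% and 10% intermittent missing, the reported SE came out about 1%, 2% and 4–5% below that from 20 step 1 draws. Only Weeks 2 and 6 are affected, because a missing Week 12 value is never intermittent.
- Step 2 runs `BY visitn` on a file with one column per visit.
- `MODELOBS` names `TREATMENT`, while the class variable is `trt`.

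**The case against.** The strongest reply is that little is lost. BOCF and the observed-data analyses already vary rescue handling. In the three main scenarios of simulation 1 they give -1.37 to -1.42 and -1.36 to -1.45, close to the -1.36 to -1.41 that analysis (1) would give if it did what its scope says. This stands, and it limits the consequence. It does not make the stated scope of analysis (1) true.

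Second, control-based fill is not uniformly harsher on the drug. Rescue follows a raised IOP, and LOCF carries that value forward. In an illustrative check (rescue 10%/20%, no dropout), control-based fill lowered rescued OTX-TP eyes from 29.0 to 26.9 mmHg and rescued PV eyes from 29.2 to 27.2. The OTX-TP change alone moves the difference by about -0.10 × 2.1 = -0.21 (simulated: -1.66 to -1.86). The PV change moves it back by about 0.20 × 2.0 = 0.40, for a net -1.45. So the attenuation comes from the excess of PV rescue. This also stands and should guide interpretation.

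Third, the monotone definition can be read as the last usable IOP, and the summary of method (b) may be shorthand. Both are fair readings, but the LOCF sentence decides the matter without them.

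Fourth, the SAP says it supersedes the protocol's statistical methods. That cannot settle a conflict between two parts of the SAP itself.

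Last, the two naming faults in the code would probably surface in programming. They are secondary. The single draw would not surface.

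**Conclusion.** The concern holds. The contradiction follows from the text alone. As the algorithm is written, analysis (1) varies the handling of dropout but not of rescue, contrary to protocol 6.3, SAP section 9 and its own description in section 13.

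The size is not established, because the documents give no rescue rates. Across the assumptions tried, the shift left out runs from about zero (OTX-TP rescued more often) to about 0.4 mmHg (PV rescued more often, with baseline-only imputation or threshold-driven rescue). The point concerns what one sensitivity analysis can be said to show. It should be corrected, but it does not threaten the primary conclusion.

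**What to change.** Choose one of two.

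1. **Make the algorithm match the scope.** In analysis (1), set post-rescue IOPs to missing instead of applying LOCF, and extend the definition of monotone missing in section 13 to visits after rescue.
2. **Make the scope match the algorithm.** Delete the post-rescue wording from section 9 and from item (1) in section 13, declare the departure from protocol 6.3 in section 19, and state that only BOCF and the observed-data analyses vary rescue handling.

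In either case, run step 1 with `NIMPUTE=20` and step 2 with `NIMPUTE=1`, by `_Imputation_` and clock time rather than `visitn`, and identify the control arm through `trt`. State whether step 2 conditions on earlier visits or on baseline only. Either is acceptable, but it changes the estimate.

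The cost is SAP wording and code. Under option 1 the sensitivity estimate may become somewhat less favourable if PV is rescued more. The primary analysis and success rule do not change. The choice is best made before unmasking.

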- *WV8* is the IOP value for the 8 Week visit;
- *WV10* is the IOP value for the 10 Week visit;
- *WV12* is the IOP value for the 12 Week visit.

Then the following SAS® code will be used to produce twenty “complete” datasets for each time point, imputing monotone missing data using a control-based pattern mixture model:

```
PROC MI DATA = mondata SEED = 48670 NIMPUTE = 20 OUT = outdata
MINIMUM = . . 0 MAXIMUM = . . 70 ROUND = . . 0.25;
BY visitn tmpntn;
CLASS trt;
MONOTONE REG(WV2_8 WV4_8 WV6_8 WV8_8 WV10_8 WV12_8 = baseline /
details);
MNAR model(WV2_8 WV4_8 WV6_8 WV8_8 WV10_8 WV12_8/ MODELOBS =
(TREATMENT="2"));
VAR trt baseline WV2_8 WV4_8 WV6_8 WV8_8 WV10_8 WV12_8;
RUN;
```

After obtaining twenty complete datasets, the data from the two MI procedures will be combined and will then be transposed to have a vertical structure with one record per subject, imputation, visit, and time point. SAS® code similar to what is previously described for multiple imputations in the primary analysis will then be employed to run the model on each dataset and combine results across imputations.

In the case that there is no missing data for a given visit and time point, observed data will be analyzed. Analyses on observed data and without MI methods will use the following statistical models:

```
ODS OUTPUT LSMEANS = outdata;
PROC MIXED DATA = indata;
```

```

CLASS trt;
MODEL IOP=trt baseline;
BY visitn tmptn
LSMEANS trt/PDIFF CL;
RUN;
    
```

where

- *IOP* is the IOP for each visit and time point;
- *visitn* is the visit number variable in numeric format;
- *tmptn* is the time point variable in numeric format;
- *baseline* is the average IOP at baseline, matched by time point;
- *trt* is the name of the treatment group variable in numeric format;
- *indata* is the dataset containing only observed data.

and

```

ODS OUTPUT STATISTICS = outdata;
PROC TTEST DATA = indata;
CLASS trt;
VAR IOP;
BY visitn tmptn;
RUN;
    
```

- *IOP* is the IOP for each visit and time point;
- *visitn* is the visit number variable in numeric format;
- *tmptn* is the time point variable in numeric format;
- *baseline* is the average IOP at baseline, matched by time point;
- *trt* is the name of the treatment group variable in numeric format;
- *indata* is the dataset containing only observed data.

Secondary Analysis

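### The control-based sensitivity analysis draws intermittent missing IOP only once, so its pooled standard errors at Weeks 2 and 6 omit that imputation uncertainty

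*SAP*

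**What the plan says.** The analysis is the first of the five sensitivity analyses in SAP v2.0, Section 13, Primary Analysis, and is reported in Table 14.2.1.3. The SAP presents it as multiple imputation, run by a process similar to the primary MCMC imputation. It has two steps.

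- **Step 1** fills the intermittent gaps: "PROC MI DATA = indata SEED = 3335891 OUT = mondata NIMPUTE=1", with "MCMC INITIAL = EM IMPUTE = MONOTONE". This writes one completed-to-monotone file.
- **Step 2** reads that file and imputes the dropout part: "PROC MI DATA = mondata SEED = 48670 NIMPUTE = 20 OUT = outdata". The BY statement is "BY visitn tmpntn"; imputation number is not a BY variable. The regression is "MONOTONE REG(WV2_8 WV4_8 WV6_8 WV8_8 WV10_8 WV12_8 = baseline", so baseline is the only predictor.

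The results from the 20 "datasets will be combined for presentation through the use of SAS® PROC MIANALYZE".

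Two definitions set the scope: "Non-monotone missing information refers to data from missed visits between any two visits at which IOP is assessed", and "Monotone missing information refers to data missing from any visits beyond a subject's final visit", the latter running up to and including Week 12.

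For contrast, the primary analysis in the same section draws every missing value 20 times. SAP v1.0 has the same 1-then-20 settings, and the v2.0 change log records only typographical and grammatical corrections to this subsection.

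**The concern.** Pooling by PROC MIANALYZE learns how uncertain an imputed value is only from its variation across the completed datasets. Here the intermittent values are identical in all 20, so they are treated as if measured. A later sentence says the data from the two imputation procedures will be combined. That cannot restore the missing component, because step 1 made only one draw.

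This is the plan's only control-based multiple-imputation check. Its purpose is to show whether the result survives a less favourable assumption about dropouts, so it should not understate its own uncertainty. Section 13, Secondary Analysis, applies all the sensitivity analyses to change and percent change from baseline, so the omission recurs there.

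**Working it through.** **Plan's own figures.** The SAP states no standard error for this analysis. Its one related figure is the power in Section 6. With 294 and 196 subjects, SD 3.75 mmHg, difference 1.5 mmHg and two-sided alpha 0.05, power is 0.9913 per time point, and 0.9913^9 = 0.924. The stated >90% is reproduced but does not bear on this point.

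**Inputs.** From the SAP: 1 draw in step 1 and 20 in step 2 (Section 13); SD 3.75, difference 1.5, 330 v 220 randomized, 10% dropout (Section 6). Not in the documents, so assumed: the intermittent-missing fraction f at a visit, and the between-visit correlation ρ.

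**Which endpoints.** A Week 2 or Week 6 value can be missing with IOP assessed before and after it. Week 12 is the last visit in the imputation list, so anything missing there is monotone. Step 2 regresses on baseline only, so the step 1 draws do not feed the Week 12 imputations.

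**Analytic size.** Rubin's total variance is T = W + (1 + 1/m)B. With m = 20 the factor is 1.05. As written, the intermittent values contribute 0 to B. Nested properly, with equal correlation between all visits, they contribute approximately

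B/W = f/(1−f) × (1−R²)/(1−ρ²), where R² = kρ²/(1+(k−1)ρ).

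Here k = 6 at 8AM (baseline and five other visits) and k = 3 at 10AM and 4PM (baseline and two other visits), because Weeks 4, 8 and 10 are measured at 8AM only.

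Example: f = 5%, ρ = 0.5, k = 6.
- R² = 1.5/3.5 = 0.4286
- (1−R²)/(1−ρ²) = 0.5714/0.75 = 0.762
- B/W = 0.0526 × 0.762 = 0.0401
- Reported SE / nested SE = 1/√(1 + 1.05 × 0.0401) = 0.980, a shortfall of 2.0%

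A second structure has correlation 0.6 between follow-up visits after adjustment for baseline. At 8AM it replaces the variance ratio by 1 − 5(0.36)/(1 + 4 × 0.6) = 0.471; at 10AM and 4PM, by 1 − 2(0.36)/1.6 = 0.55.

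| f | Shortfall, ρ 0.3–0.7, all clock times | Shortfall, baseline-adjusted 0.6 (8AM to 10AM/4PM) |
|---|---|---|
| 2% | 0.7–1.0% | 0.5–0.6% |
| 3% | 1.1–1.5% | 0.8–0.9% |
| 5% | 1.8–2.4% | 1.3–1.5% |
| 10% | 3.7–4.9% | 2.6–3.1% |

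**Simulation of both orders** (330 v 220, 10% dropout, 8AM series, ρ = 0.5, 132 replicates per row). Mean pooled SE of the treatment difference in mmHg, as written → nested:

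| f | Week 2 | Week 6 | Week 12 |
|---|---|---|---|
| 2% | 0.2859 → 0.2881 (−0.8%) | 0.2919 → 0.2945 (−0.9%) | 0.3025 → 0.3025 |
| 5% | 0.2859 → 0.2922 (−2.2%) | 0.2922 → 0.2973 (−1.7%) | 0.3067 → 0.3068 |
| 10% | 0.2860 → 0.2984 (−4.2%) | 0.2922 → 0.3036 (−3.8%) | 0.3140 → 0.3142 |

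A separate simulation at baseline-adjusted correlation 0.6 (150 replicates) gave about 0.7%, 1.1% and 2.5% at f = 3%, 5% and 10%, with no change at Week 12.

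**Noise in the estimate.** One draw instead of an average over 20 also adds variance to the point estimate, so its own variance is about W + 2B. Against that, the shortfall at f = 5% is 3.4–4.5% (ρ 0.3–0.7).

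**In p-value terms.** An SE ratio r turns a properly computed p above 0.05 into a reported p below 0.05 only if the proper |z| exceeds 1.96r. For r = 0.989, 0.975 and 0.958 the upper limits of the proper p are about 0.053, 0.056 and 0.060.

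**The case against.** The strongest reply is that this cannot change the planned conclusion. The success rule rests on the primary analysis, which draws everything 20 times. No pass/fail rule attaches to Table 14.2.1.3, and the effect is small at plausible rates. Some gaps also close before step 1: unscheduled data replace missing scheduled values (Section 9), and post-rescue values are filled by LOCF. All of this stands, and it limits the weight of the point. It does not make the code proper multiple imputation.

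A reader might also infer more than the documents support:

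- *That the 20 datasets are copies.* They are not; the dropout values are drawn 20 times. Only the intermittent values are shared.
- *That the error always favours OTX-TP.* It does so on average. In a simulation at ρ = 0.5, 5% intermittent missing and 10% dropout (120 replicates), the as-written SE was smaller in 99% of replicates at Week 2 and 83% at Week 6. The test statistic favoured OTX-TP more than the nested version in only 75% and 64%.
- *That the intervals are shown to under-cover.* They are not; the comparison is between two pooled SEs. Rubin's variance looked conservative for the control-based dropout part (Week 12 at f = 2%: reported 0.3025, empirical SD 0.279). That may offset some of the shortfall at Week 6, and least at Week 2. With 132 replicates the empirical SDs carry about 6% Monte Carlo error, so the extent is not settled.
- *That this is the plan's only departure from missing at random.* BOCF also departs from it, by returning dropouts to baseline.

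**Conclusion.** The point holds as a coding error in one sensitivity analysis. As written, the pooled standard errors at the Week 2 and Week 6 endpoints leave out the imputation uncertainty of the intermittent values. Week 12 is unaffected, and so is any visit and time point without such gaps. The size rests on assumed missing rates and correlations. Taking the two correlation structures and the simulations together, the average shortfall against nested imputation is about 0.5–1% at 2% missing, 1–2.4% at 5% and 2.5–5% at 10%, plus seed-dependent noise in the estimate. It would matter only for a result near p = 0.05. The reading that it casts doubt on the primary efficacy result is not supported. The correction should still be made, because the SAP describes the method as multiple imputation and for these values it is not.

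**What to change.** Before unmasking, change the printed code as follows:

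- In step 1, set NIMPUTE to 20 and keep the MCMC option that imputes only to a monotone pattern.
- In step 2, set NIMPUTE to 1 and run it by _Imputation_ and time point in place of the present BY line. Visits are columns in that file, so visit number cannot serve as a BY variable there.
- In the same block, align the variable names. The MNAR statement names TREATMENT where the class variable is trt, and the visit variables carry only the 8AM suffix.
- Pool the resulting 20 datasets with PROC MIANALYZE, and add one sentence to the text saying that each step 1 draw is completed once.

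The cost is minor code edits and slightly wider confidence intervals at Weeks 2 and 6. No new data are needed.
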